## 5.0 Treatment plan: atorvastatin vs placebo

After randomization, patients on the statin arm will start the assigned study drug (atorvastatin) for a total of 9 months, in addition to the standard of care (anticoagulation). Atorvastatin will be prescribed through patients' pharmacy of choice. It will be taken once a day in a tablet form. Pill count and patient self-report compliance diary will be reviewed at each visit. All the attempts will be made to continue atorvastatin for entire 9 months, however, if a patient needs to stop atorvastatin prior to the intended period for any reasons (for example, side effects), it will be documented, but they are allowed to remain in the study for blood tests and clinical follow up. At the end of the study, the decision of whether patients should remain on atorvastatin or not will be left to the treating physicians.

## 6.0 Study calendar

	Initial visit	3 month 	9 month 
Singed informed consent	x		
Medical/treatment history	x	x	x
Physical examination	x	x	x
Vital signs	x	x	x
CBC with diff	x	x	x
Chemistry, including liver function tests	x	x	x
Fasting lipid profiles	x	x	x
hs-CRP	x	x	x
D-dimer	x	x	x
Urine <math>\beta</math>-hCG	x		
Thrombin generation assay	x	x	x
IL-6, IL-8, TNF-<math>\alpha</math>	x	x	x
Lipidomic profiles	x	x	x
Doppler ultrasound of bilateral lower extremities		x	
Prescription of statins	x	x	

All scheduled visits are allowed a window of +/- 21 days

CBC includes: white blood cells with differential, hemoglobin, red blood cells, and platelets

Chemistry and liver function tests include: sodium, potassium, carbon dioxide, glucose, BUN, creatinine, calcium, total protein, albumin, bilirubin, alkaline phosphatase, AST and ALT

Required only in women of child-bearing potential

Lipidomic profiles includes free fatty acids, lipoprotein-associated phospholipase A2, pro-inflammatory eicosanoids

Prescription of statins only in the statin arm

## 7.0 **Outcome Criteria**

### 7.1 **Recurrent venous thromboembolism**

7.1.1 Recurrent pulmonary embolism will be diagnosed when:

- a) New filling defect(s) is/are seen in CT angiogram of chest or pulmonary angiography
- b) A new high probability on ventilation-perfusion lung scan.

7.1.2 Recurrent deep vein thrombosis will be diagnosed when:

- a) New filling defect(s) is/are seen in venography or new uncompressible segments seen on vascular Doppler ultrasound in a previously uninvolvled limb
- b) In the limb with a previous VTE, new filling defect(s) in venography or new uncompressible segments in vascular Doppler ultrasound that is clearly extending from the prior thrombosis or involving a new venous segment

### 7.2 **Arterial thromboembolism**

7.2.1 Myocardial infarction:

Myocardial infarction will be diagnosed if at least two of the following criteria are met: a history of typical ischemic pain lasting for at least 20 minutes and unresponsive to sublingual nitrates (if given), new elevation of cardiac enzymes (creatinine kinase or its MB fraction) to more than twice the ULN or troponin value, new EKG changes including new persistent ST/T changes, new bundle branch block or new Q waves in at least two consecutive leads.

7.2.2 Cerebral vascular accidents:

Cerebral vascular accidents (CVA) is a clinical syndrome of rapid development of focal or global loss of brain function, lasting more than 24 hours, thought to be vascular in origin, and/or leading to neurological damages or early death. It is expected that CT or MRI scans will be performed to confirm the diagnosis in most cases.

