## **11.0 Safety Monitoring During Study**

11.1 To ensure the safety of all patients enrolled on this study, careful monitoring and follow-ups for all patients will be important aspects of this study. Patients will be monitored closely with laboratory and clinical evaluations at regular intervals defined in the study protocol.

11.2 At each visit (enrollment, 3 and 9 months), patients will be evaluated by physicians and study personnel for side effects of statins and anticoagulation. The management of side effects from statins will follow the routine practice for patients who are prescribed with statins for other medical problems, and will be left to the discretion of the treating physicians, but the study team and PI will be available for any assistance if questions of the optimal management of adverse events were to arise. Liver function tests will be obtained prior to and at each follow-up visit. Creatine kinase (CK) test will not be collected without symptoms, but will be collected if patients were to develop symptoms of muscle pain or weakness. Patients with new onset of transaminitis or CK above three times of upper limit of normal or significant symptoms will be taken off statins. Their abnormal laboratory tests will be monitored at least every 2 weeks, more frequently if needed, until the abnormalities resolve. Patients will only resume statins if their symptoms resolve, blood tests normalize, and if patients are willing to resume treatment. Recurrent test abnormality or symptoms will require permanent discontinuation of statins.

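### Section 7.2.1 lets total creatine kinase, which section 11.2 treats as a possible statin effect, supply one of the two criteria for myocardial infarction; a small bias against the statin is possible

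*Combined protocol and SAP*

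**What the plan says.** Section 7.2.1 sets a two-of-three rule: "Myocardial infarction will be diagnosed if at least two of the following criteria are met". The criteria are:

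- typical ischemic pain of 20 minutes or more;
- "new elevation of cardiac enzymes (creatinine kinase or its MB fraction) to more than twice the ULN or troponin value" (read here as creatine kinase);
- "new EKG changes including new persistent ST/T changes, new bundle branch block or new Q waves in at least two consecutive leads".

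In the second criterion, total CK is an alternative to its MB fraction, and both are alternatives to troponin. No cut-off is clearly attached to troponin.

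Section 11.2, on side effects of statins and anticoagulation, says: "Creatine kinase (CK) test will not be collected without symptoms, but will be collected if patients were to develop symptoms of muscle pain or weakness". It continues: "Patients with new onset of transaminitis or CK above three times of upper limit of normal or significant symptoms will be taken off statins".

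MI is one of the two arterial events defined in section 7.2. Objective 1.2.2 compares the arterial event rate between arms, and section 20.0 analyses secondary endpoints by chi-square or Fisher's exact test, with descriptive statistics by arm. Section 1.0 describes the study as open label.

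**The concern.** An outcome criterion should not move with the randomised treatment except through the disease it is meant to detect. Here the protocol's own safety section ties raised CK to the statin, while the outcome section accepts the same measurement as evidence of cardiac injury. For a patient whose CK is raised by the drug, the two-criterion test for MI becomes a one-criterion test. If such rises are found more often on atorvastatin, misclassification is unequal between arms and runs against the statin.

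The remaining criterion is not fully protected either. A history of typical ischemic pain is a clinical judgement, the trial is open label, and the text describes no blinded adjudication of arterial events. What is at stake is the estimate for one secondary objective. The primary thrombin endpoints are unaffected.

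**Working it through.** **The plan's own figures.** No event rate or power is stated for arterial events. The only power statement (section 20.0) is for the thrombin endpoints: 33 evaluable per arm, 0.7 SD, two-sided alpha 0.05, 80% power. It reproduces: n = 2(1.96 + 0.84)²/0.7² = 32.0, which rounds up to 33 per arm, and t-test power at 33 per arm is 0.800. The point below does not depend on it. Target enrollment is 40 per arm.

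**When does total CK decide the diagnosis?** Take a patient without a true MI, with total CK above 2 x ULN and no qualifying CK-MB or troponin.

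| Other criteria met (pain, EKG) | Criteria met with CK | Criteria met without CK | Effect of CK |
|---|---|---|---|
| 0 | 1 of 3 | 0 of 3 | none; not an MI |
| 1 | 2 of 3 | 1 of 3 | turns a non-event into an MI |
| 2 | 3 of 3 | 2 of 3 | none; already an MI |

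Only the middle row creates a false event.

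**How often?** The documents give no rates, so these ranges are assumptions:

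- c = probability that a statin-arm patient has a measured CK above 2 x ULN: 1% to 10%;
- s = probability that a further criterion is met without a true MI, given such a CK: 5% to 20%.

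Expected false MIs among 40 = 40 × c × s. Chance of at least one = 1 − (1 − c × s)^40.

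| c | s | Expected false MIs | Chance of at least one |
|---|---|---|---|
| 1% | 5% | 0.02 | 2% |
| 5% | 10% | 0.20 | 18% |
| 10% | 10% | 0.40 | 33% |
| 10% | 20% | 0.80 | 55% |

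These are gross counts in the statin arm. The expected between-arm bias is s × (c in the statin arm − c in the control arm), if s is the same in both arms. It is largest when the control value of c is zero. It then runs from 0.01 × 0.05 = 0.05 percentage points to 0.10 × 0.20 = 2 percentage points, and any CK rises in controls reduce it.

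**What one case would do.** 1/40 = 2.5 percentage points on the statin arm's rate. For a events v 0 with 40 per arm, the two-sided Fisher p is 2 × C(40,a)/C(80,a):

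- 1 v 0: p = 1.00
- 2 v 0: p = 0.49
- 5 v 0: p = 0.055
- 6 v 0: p = 0.026

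**The case against.** The strongest reply is that the chain from drug to false MI is long. A CK rise meets one criterion and two are needed. The muscle pain or weakness that prompts a CK test is not typical ischemic pain, and no EKG is in the study calendar. CK matters only when exactly one cardiac criterion is present without an infarction and CK happens to be raised as well. The endpoint is secondary, in a single-center pilot sized for thrombin endpoints. All of this stands, and it is why the point is minor.

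Four stronger readings are tempting, and the documents do not support them:

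- *False events would arise in the statin arm only.* The CK testing rule in section 11.2 speaks of patients and names no arm, and CK could be raised or measured in controls. The supportable wording is somewhat more often in the statin arm.
- *The cut-offs of 2 x ULN in 7.2.1 and 3 x ULN in 11.2 contradict each other.* One is part of an outcome definition and the other is a safety trigger. They serve different purposes and can differ.
- *The lack of a scheduled enrolment CK adds to the bias.* CK is absent from the calendar and laboratory lists, so a new rise has no planned comparison value, but this applies equally to both arms. CK-MB and troponin are not scheduled either.
- *The missing troponin cut-off biases the comparison.* It is unclear drafting that affects both arms alike.

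What the reply does not remove is that one of three MI criteria depends on a marker the protocol itself links to the randomised drug, when more specific alternatives already stand in the same sentence.

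**Conclusion.** The point holds as a low-severity weakness in an outcome definition. Total CK above 2 x ULN meets the enzyme criterion although section 11.2 treats raised CK as a possible statin effect, so that criterion is not independent of arm. Any resulting bias in objective 1.2.2 would run slightly against the statin.

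Under the assumed rates, fewer than one false MI is expected among 40 statin patients (0.02 to 0.8). The top of that range needs both assumptions at their extremes. No significance test is likely to turn on it, since about 6 v 0 would be needed for p below 0.05. The practical risk is to the descriptive estimate: if true arterial events are few or none, which is also an assumption, a single false case could be the whole observed difference.

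**What to change.** In the outcome definition of 7.2.1, remove total creatine kinase from the enzyme criterion. Suggested wording: *a new rise in CK-MB above twice the ULN, or a new troponin value above the local laboratory's upper reference limit; an isolated rise in total creatine kinase does not count.* This also gives troponin a cut-off and corrects the enzyme's name.

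The change is one sentence. It adds no tests or visits and leaves the safety monitoring in 11.2 untouched. The downside is that an MI documented only by total CK would no longer qualify on that marker, although it would still count if both the pain and EKG criteria were met.

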### 1.2 Secondary Objectives

1.2.1 To determine the composite rate of recurrent VTE and VTE related mortality in patients in the statin arm as compared to no statin arm.

1.2.2 To determine the rate of arterial thrombotic events in patients in the statin arm as compared to no statin arm.

1.2.3 To determine the rate of major, non-major, and all hemorrhages defined by the ISTH (International Society on Thrombosis and Haemostasis) criteria (see section 7.3) in patients in the statin arm as compared to no statin arm.

- 1.2.4 To evaluate the changes in proposed hemostatic, inflammatory, and lipidomic biomarkers at 3 and 9 months compared to upon enrollment in patients in both arms.
- 1.2.5 To determine the rate of residual vein obstruction by Doppler ultrasound at 3 months in patients in the statin arm as compared to no statin arm.
- 1.2.6 To determine the rate of clinical post-thrombotic syndrome (PTS), as objectively evaluated with Villalta scoring system in patients in the statin arm as compared to no statin arm.

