### **3.2 Inclusion Criteria**

- 3.2.1 At least 18 years old
- 3.2.2 A diagnosis of proximal DVT (proximal to and including popliteal vein), with or without PE, confirmed by objective imaging studies, such as Doppler ultrasound, venograms (for DVT) and/or computer tomography, angiograms, ventilation-perfusion scan (for PE)
- 3.2.3 Treated with warfarin or rivaroxaban as anticoagulation (short-term bridging with heparin or lovenox, if needed is allowed)

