### 7.3 **Bleeding**

7.3.1 Major bleeding will be defined as:

- a) Bleeding into critical organs such as central nervous system, retroperitoneum
- b) Bleeding requiring emergent intervention or surgery for hemostasis
- c) Bleeding requiring at least 2 units of packed red blood cell transfusion
- d) Bleeding leading to at least 2 points drop in hemoglobin from baseline
- e) Bleeding requiring hospital admission for intervention

7.3.2 Non-major bleeding is defined as any other bleeding reported by patients but not otherwise meeting the above listed criteria for major bleeding

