**20.0 Statistical Analysis**

At least 66 evaluable patients will be randomized (1:1 allocation, 33 evaluable patients in each arm) into "anticoagulation" versus "anticoagulation +atorvastatin" arms. The primary endpoints are thrombin peak and thrombin generation. Based on the published data, we anticipate an 80% power to detect an effect size of 0.7 standard deviations in the reduction of thrombin peak or thrombin generation between the two arms with two-side alpha of 0.05 using a two-sample t test. An overall alpha of 0.1 for this pilot study was split into 0.05 for each endpoint (thrombin peak and thrombin generation) using Bonferroni method. Considering possible drop-outs, our target enrollment will be 80 patients, with 40 on each arm.

All data will be collected on study-approved data collection forms and entered into Research Electronic Data Capture (REDCap), which is a secure, web-based application designed to support data capture for research studies by building and managing online surveys and databases. The system was built with the help of the OSU Research Informatics Services.

Descriptive statistics (i.e. means, standard deviations, 95% confidence intervals for continuous variables, and frequencies for discrete data) and graphical analyses will be used for all clinical outcomes, demographics, VTE related events, laboratory results, and adverse events for each arm. The secondary endpoints will be compared between the two arms using chi-square test or Fisher's exact test, whichever is appropriate. The associations between treatment type and the change in biomarkers will be evaluated using two-sample t test. Log-transform will be used if necessary. Linear mixed models will be used to study the associations between the primary endpoints and treatment, and trend across time. The interaction term "arm x time" will be included in the model to study whether the two treatment arms have different "behavior" across time. Potential confounders will be included in the models. Thrombin peak concentration and

endogenous thrombin potential at 9 months will be compared between the patients on anticoagulation and those off anticoagulation.

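### The stroke definition in 7.2.2 does not exclude haemorrhage, so an intracranial bleed can enter the arterial thrombotic count as well as the major-bleeding count (minor effect)

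*Combined protocol and SAP*

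**What the plan says.** Secondary objective 1.2.2 reads: "To determine the rate of arterial thrombotic events in patients in the statin arm as compared to no statin arm". Section 7.2, headed as arterial thromboembolism, supplies the outcome criteria in two parts: myocardial infarction (7.2.1) and cerebral vascular accident (7.2.2). The second begins "Cerebral vascular accidents (CVA) is a clinical syndrome of rapid development of focal or global loss of brain function, lasting more than 24 hours" and continues "thought to be vascular in origin, and/or leading to neurological damages or early death". On imaging it adds: "It is expected that CT or MRI scans will be performed to confirm the diagnosis in most cases".

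Bleeding is a separate objective, 1.2.3: "To determine the rate of major, non-major, and all hemorrhages defined by the ISTH". Under 7.3.1(a), major bleeding includes "Bleeding into critical organs such as central nervous system, retroperitoneum".

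Inclusion criterion 3.2.3 requires that patients be "Treated with warfarin or rivaroxaban as anticoagulation". Section 20.0 states: "The secondary endpoints will be compared between the two arms using chi-square test", with Fisher's exact test as the alternative.

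**The concern.** Objective 1.2.2 is about thrombosis, but the rule that identifies its stroke events does not ask for ischaemia, infarction, thrombus or embolus, and does not set haemorrhage aside. A bleed into the brain is vascular in origin. If it starts suddenly and leaves a deficit for more than a day, it satisfies 7.2.2 as written.

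The same event is a major bleed under 7.3.1(a). In an anticoagulated population this overlap is foreseeable. Arterial thrombosis and haemorrhage are separate objectives because they answer different questions, and a treatment could move them in opposite directions. A bleed filed under 7.2.2 would put a bleeding complication into the thrombotic comparison between arms. The trial is open-label and describes no independent event adjudication, so an ambiguous event would be classified by staff who know the allocation. With few events expected, one misfiled case could be the whole arterial count.

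**Working it through.** **Reading the two rules against one event.** Take an intracerebral haemorrhage of sudden onset with a deficit lasting more than 24 hours.

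| Requirement | Met by this event? |
|---|---|
| 7.2.2: rapid loss of brain function, focal or global | Yes |
| 7.2.2: duration over 24 hours | Yes |
| 7.2.2: presumed vascular cause | Yes |
| 7.2.2: ischaemic or thrombotic mechanism | Not asked for |
| 7.2.2: haemorrhage excluded on imaging | Not asked for |
| 7.3.1(a): bleeding into the central nervous system | Yes |

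No section assigns an event that meets both rules to one of them. The neighbouring criteria are more specific about what must be shown: 7.1 asks for new filling defects, new non-compressible segments or a new high-probability scan, and 7.2.1 asks for two of ischaemic pain, enzyme rise and EKG change.

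**The plan's own figure.** Section 20.0 gives 33 evaluable patients per arm for 80% power at 0.7 SD, two-sided alpha 0.05, two-sample t test. Exact t-test power at 33 per arm is 79.97%, so the figure reproduces. It concerns the thrombin endpoints only and does not depend on the stroke definition.

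**Effect of one misfiled bleed.** Inputs: 33 evaluable or 40 enrolled per arm (Section 20.0); one bleed entered under 7.2.2 and no other arterial event in either arm.

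- Shift in one arm's rate: 1/33 = 3.03 percentage points; 1/40 = 2.50.
- 95% CI for the difference d = p1 − p2 (Newcombe, from Wilson limits l and u): lower = d − √[(p1 − l1)² + (u2 − p2)²]; upper = d + √[(u1 − p1)² + (p2 − l2)²].
  - 33 per arm: Wilson limits are 0.54% to 15.32% for 1/33 and 0% to 10.43% for 0/33. Lower = 3.03 − √(2.49² + 10.43²) = −7.7; upper = 3.03 + √(12.29² + 0²) = 15.3.
  - 40 per arm: Wilson limits are 0.44% to 12.88% for 1/40 and 0% to 8.76% for 0/40. Lower = 2.50 − √(2.06² + 8.76²) = −6.5; upper = 2.50 + √(10.38² + 0²) = 12.9.
- Fisher's exact test, two-sided, 1 v 0: p = 1.00 at both sizes.
- More extreme cases at 40 per arm: 2 v 0 gives p = 0.49; 3 v 0 gives p = 0.24.

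**How often it might arise.** The documents give no intracranial-bleed rate. For an assumed 9-month risk r of a qualifying bleed among the 80 patients to be enrolled, the expected number is 80r and the chance of at least one is 1 − (1 − r)^80.

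| Assumed r | Expected events | Chance of at least one |
|---|---|---|
| 0.1% | 0.08 | 7.7% |
| 0.5% | 0.4 | 33.0% |
| 1% | 0.8 | 55.2% |

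These are chances that a qualifying bleed occurs, not that it is misclassified. The second must be no larger than the first and cannot be estimated from the documents.

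**The case against.** The strongest reply is that 7.2.2 should be read with its heading and its objective. The section is about arterial thromboembolism, objective 1.2.2 counts thrombotic events, and 7.3.1(a) names central nervous system bleeding as its own outcome. Read together, these already send a bleed to 7.3, and the 1.2.2 count goes wrong only if someone records a recognised haemorrhage as thrombosis. Imaging is also expected in most cases, so most strokes would be typed correctly in practice.

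This establishes the intention, and it makes misfiling less likely than the occurrence figures above. It does not supply the missing criterion. A heading is not a diagnostic rule. The scan is there to confirm a stroke as defined, and that definition includes a bleed. Nothing says that a scan showing haemorrhage removes the event from 7.2.

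Two further points stand. First, the assumed bleed risks have no anchor in the documents, and exposure may not be uniform, because Section 20.0 foresees some patients off anticoagulation at 9 months. Second, the consequence is slight: this is a secondary count with no power calculation of its own, in a pilot. It can also be argued that one added word would be enough and that separate reporting of untyped strokes is more than is needed. That is a fair view of proportion, but one word alone would leave strokes without imaging unassigned.

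**Conclusion.** The concern holds as a minor one, for the sponsor to consider. Applied literally, 7.2.2 admits an intracranial bleed to the arterial thrombotic endpoint, and no other text takes it out. If one such bleed is the only arterial event, the between-arm difference reads 3.0 points (95% CI −7.7 to 15.3) at 33 per arm or 2.5 points (−6.5 to 12.9) at 40 per arm, where it should read zero. It distorts a tabulated count and does not produce a significant result.

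No composite adds arterial events to bleeds, so no single endpoint counts the event twice. The size of the shift rests only on the planned arm sizes. The frequency is unknown, and the illustration above depends wholly on the assumed risks. The reading of the text does not depend on them.

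**What to change.** Reword 7.2.2 so that the events counted for objective 1.2.2 are non-haemorrhagic (ischaemic) strokes, meaning that the CT or MRI already expected does not show bleeding as the cause of the deficit. State that intracranial haemorrhage is counted only under 7.3. Record strokes without imaging as type undetermined, and show the 1.2.2 count with and without them. Sections 7.1, 7.2.1 and 7.3 need no change.

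The cost is a change of wording and one recorded stroke type per cerebral vascular accident; the event form was not available for review. No scans, visits or assessors are added, and no treatment rule is tied to this definition. The downside is that a few strokes may remain of undetermined type.
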